## Appendix B      ECOG Performance Status

Grade	Activity Level
0	Fully active, able to carry on all pre-disease performance without restriction.
1	Restricted in physically strenuous activity but ambulatory and able to carry out work of a light or sedentary nature (eg, light housework, office work).
2	Ambulatory and capable of all self-care but unable to carry out any work activities. Up and about more than 50% of waking hours.
3	Capable of only limited self-care, confined to bed or chair more than 50% of waking hours.
4	Completely disabled cannot carry on any self-care, totally confined to bed or chair.
5	Death.

## **Appendix C Response Evaluation Criteria in Solid Tumors Version 1.1 (RECIST Version 1.1)**

Quick Reference:

<http://ctep.cancer.gov/guidelines/recist.html>

### **Patient Eligibility**

Only patients with measurable disease at baseline should be included in protocols where objective tumor response is the primary endpoint. Measurable disease is defined as the presence of at least one measurable lesion.

In studies where the primary endpoint is tumor progression (either time to progression or proportion with progression at a fixed date), the protocol must specify if entry is restricted to those with measurable disease or whether patients having non-measurable disease only are also eligible.

### **Methods of Assessment**

- The same method of assessment and the same technique should be used to characterize each identified and reported lesion at baseline and during follow-up. CT is the best currently available and reproducible method to measure lesions selected for response assessment. MRI is also acceptable in certain situations (eg, for body scans but not for lung).
- Lesions on a chest X-ray may be considered measurable lesions if they are clearly defined and surrounded by aerated lung. However, CT is preferable.
- Clinical lesions will only be considered measurable when they are superficial and  $\geq 10$  mm in diameter, as assessed using calipers. For the case of skin lesions, documentation by color photography, including a ruler to estimate the size of the lesion, is recommended.
- Ultrasound (US) should not be used to measure tumor lesions.
- Tumor markers alone cannot be used to assess response. If markers are initially above the upper normal limit, they must normalize for a patient to be considered in complete response.
- Cytology and histology can be used in rare cases (eg, for evaluation of residual masses to differentiate between Partial Response and Complete Response or evaluation of new or enlarging effusions to differentiate between Progressive Disease and Response/Stable Disease).
- Use of endoscopy and laparoscopy is not advised. However, they can be used to confirm complete pathological response.

### **Baseline Disease Assessment**

All baseline evaluations should be performed as closely as possible to the beginning of treatment and never more than 4 weeks before the beginning of the treatment.

## Measurable lesions

Must be accurately measured in at least one dimension (longest diameter in the plane of measurement is to be recorded) with a minimum size of:

- 10 mm by CT scan (CT scan slice thickness no greater than 5 mm; when CT scans have slice thickness >5 mm, the minimum size should be twice the slice thickness).
- 10 mm caliper measurement by clinical exam (lesions that cannot be accurately measured with calipers should be recorded as non-measurable).
- 20 mm by chest X-ray.

**Malignant Lymph Nodes:** To be considered pathologically enlarged and measurable, a lymph node must be  $\geq 15$  mm in short axis when assessed by CT scan (CT scan slice thickness is recommended to be no greater than 5 mm). At baseline and in follow-up, only the short axis will be measured and followed.

Lytic bone lesions or mixed lytic-blastic lesions with identifiable soft tissue components that can be evaluated by cross-sectional imaging techniques such as CT or MRI can be considered measurable if the soft tissue component meets the definition of measurability described above.

“Cystic lesions” thought to represent cystic metastases can be considered measurable if they meet the definition of measurability described above. However, if non-cystic lesions are present in the same patient, these are preferred for selection as target lesions.

## Non-measurable Lesions

Non-measurable lesions are all other lesions, including small lesions (longest diameter <10 mm or pathological lymph nodes with 10 to <15 mm short axis), as well as truly non-measurable lesions. Lesions considered truly non-measurable include: leptomeningeal disease, ascites, pleural or pericardial effusion, inflammatory breast disease, lymphangitic involvement of skin or lung, abdominal masses/abdominal organomegaly identified by physical exam that is not measurable by reproducible imaging techniques. Blastic bone lesions are non-measurable.

Lesions with prior local treatment, such as those situated in a previously irradiated area or in an area treated with other loco-regional therapy, are usually not considered measurable unless there has been demonstrated progression in the lesion. Study protocols should detail the conditions under which such lesions would be considered measurable.

## Target Lesions

- All measurable lesions up to a maximum of two lesions per organ and five lesions in total, representative of all involved organs, should be identified as target lesions and recorded and measured at baseline.
- Target lesions should be selected on the basis of their size (lesions with the longest diameter) and be representative of all involved organs, as well as their suitability for reproducible repeated measurements.
- All measurements should be recorded in metric notation using calipers if clinically assessed.

A sum of the diameters (longest for non-nodal lesions, short axis for nodal lesions) for all target lesions will be calculated and reported as the baseline sum diameters, which will be used as reference to further characterize any objective tumor regression in the measurable dimension of the disease. If lymph nodes are to be included in the sum, only the short axis will contribute.

### **Non-target Lesions**

All lesions (or sites of disease) not identified as target lesions, including pathological lymph nodes and all non-measurable lesions, should be identified as non-target lesions and be recorded at baseline. Measurements of these lesions are not required and they should be followed as “present,” “absent,” or in rare cases, “unequivocal progression.”

### **Evaluation of Target Lesions**

**Complete Response (CR):** Disappearance of all target lesions. Any pathological lymph nodes (whether target or non-target) must have reduction in short axis to <10 mm.

**Partial Response (PR):** At least a 30% decrease in the sum of diameters of target lesions, taking as reference the baseline sum of diameters.

**Progressive Disease (PD):** At least a 20% increase in the sum of diameters of target lesions, taking as reference the smallest sum on study (this may include the baseline sum). The sum must also demonstrate an absolute increase of at least 5 mm.

**Stable Disease (SD):** Neither sufficient shrinkage to qualify for PR nor sufficient increase to qualify for PD.

### **Special Notes on the Assessment of Target Lesions**

Lymph nodes identified, as target lesions should always have the actual short axis measurement recorded even if the nodes regress to below 10 mm on study. When lymph nodes are included as target lesions, the “sum” of lesions may not be zero even if complete response criteria are met since a normal lymph node is defined as having a short axis of <10 mm.

**Target lesions that become “too small to measure”:** While on study, all lesions (nodal and non-nodal) recorded at baseline should have their actual measurements recorded at each subsequent evaluation, even when very small. However, sometimes lesions or lymph nodes become so faint on a CT scan that the radiologist may not feel comfortable assigning an exact measure and may report them as being “too small to measure”, in which case a default value of 5 mm should be assigned.

**Lesions that split or coalesce on treatment:** When non-nodal lesions “fragment,” the longest diameters of the fragmented portions should be added together to calculate the target lesion sum. Similarly, as lesions coalesce, a plane between them may be maintained that would aid in obtaining maximal diameter measurements of each individual lesion. If the lesions have truly coalesced such that they are no longer separable, the vector of the longest diameter in this instance should be the maximal longest diameter for the “coalesced lesion”.

## Evaluation of Non-Target Lesions

**Complete Response (CR):** Disappearance of all non-target lesions and normalization of tumor marker levels. All lymph nodes must be non-pathological in size (<10 mm short axis).

**Non-CR / Non-PD:** Persistence of one or more non-target lesion(s) and/or maintenance of tumor marker levels above normal limits.

**Progressive Disease (PD):** Unequivocal progression of existing non-target lesions. When patient has measurable disease, to achieve “unequivocal progression” on the basis of the non-target disease, there must be an overall level of substantial worsening in non-target disease such that, even in presence of SD or PR in target disease, the overall tumor burden has increased sufficiently to merit discontinuation of therapy. A modest “increase” in the size of one or more non-target lesions is usually not sufficient to qualify for unequivocal progression status.

**When patient has only non-measurable disease:** There is no measurable disease assessment to factor into the interpretation of an increase in non-measurable disease burden. Because worsening in non-target disease cannot be easily quantified, a useful test that can be applied is to consider if the increase in overall disease burden based on change in non-measurable disease is comparable in magnitude to the increase that would be required to declare PD for measurable disease. Examples include an increase in a pleural effusion from “trace” to “large” or an increase in lymphangitic disease from localized to widespread.

## New Lesions

The appearance of new malignant lesions denotes disease progression:

- The finding of a new lesion should be unequivocal (ie, not attributable to differences in scanning technique, change in imaging modality or findings thought to represent something other than tumor, especially when the patient’s baseline lesions show partial or complete response).
- If a new lesion is equivocal, for example because of its small size, continued therapy and follow-up evaluation will clarify if it represents truly new disease. If repeat scans confirm there is definitely a new lesion, then progression should be declared using the date of the initial scan.
- A lesion identified on a follow-up study in an anatomical location that was not scanned at baseline is considered a new lesion and disease progression.

It is sometimes reasonable to incorporate the use of F-fluorodeoxyglucose positron emission tomography (FDG-PET) scanning to complement CT in assessment of progression (particularly possible “new” disease). New lesions on the basis of FDG-PET imaging can be identified according to the following algorithm:

Negative FDG-PET at baseline, with a positive FDG-PET at follow-up is PD based on a No FDG-PET at baseline and a positive FDG-PET at follow-up:

- If the positive FDG-PET at follow-up corresponds to a new site of disease confirmed by CT, this is PD.

- If the positive FDG-PET at follow-up is not confirmed as a new site of disease on CT, additional follow-up CT scans are needed to determine if there is truly progression occurring at that site (if so, the date of PD will be the date of the initial abnormal FDG-PET scan).
- If the positive FDG-PET at follow-up corresponds to a pre-existing site of disease on CT that is not progressing on the basis of the anatomic images, this is not PD.

### Time Point Response

Below is a summary of the overall response status calculation at each time point for patients who have measurable disease at baseline: Patients with target (+/- non-target) disease.

Target lesions	Non-target lesions	New lesions	Overall Response
CR	CR	No	CR
CR	Non-CR /non-PD	No	PR
CR	NE	No	PR
PR	Non-PD or NE	No	PR
SD	Non-PD NE	No	SD
Not all evaluated	Non-PD	No	NE
PD	Any	Yes or No	PD
Any	PD	Yes or No	PD
Any	Any	Yes	PD

CR = Complete Response; PR = Partial Response; SD = Stable Disease; PD = Progressive Disease; NE = Not Evaluable

### Confirmation

In non-randomized trials where response is the primary endpoint, confirmation of PR and CR is required to ensure responses identified are not the result of measurement error. This will also permit appropriate interpretation of results in the context of historical data where response has traditionally required confirmation in such trials. However, in all other circumstances, (ie, in randomized phase 2 or 3 trials or studies where stable disease or progression are the primary endpoints), confirmation of response is not required since it will not add value to the interpretation of trial results. However, elimination of the requirement for response confirmation may increase the importance of central review to protect against bias, in particular in studies that are not blinded.

In the case of SD, measurements must have met the SD criteria at least once after study entry at a minimum interval (in general not less than 6–8 weeks) that is defined in the study protocol.

### Missing Assessments and Inevaluable Designation

When no imaging/measurement is done at all at a particular time point, the patient is not evaluable (NE) at that time point. If only a subset of lesion measurements are made at an assessment, usually the case is also considered NE at that time point, unless a convincing argument can be made that the contribution of the individual missing lesion(s) would not change the assigned time point response. This would most likely happen in the case of PD.

### Reporting of Results

- All patients included in the study must be assessed for response to treatment, even if there are major protocol treatment deviations or if they are ineligible. Each patient

will be assigned one of the following categories: 1) complete response, 2) partial response, 3) stable disease, 4) progressive disease, 5) early death from malignant disease, 6) early death from toxicity, 7) early death because of other cause, or 9) unknown (not assessable, insufficient data).

- All the patients who met the eligibility criteria should be included in the main analysis of the response rate. Patients in response categories 4-9 should be considered as failing to respond to treatment (disease progression). Thus, an incorrect treatment schedule or drug administration does not result in exclusion from the analysis of the response rate. Precise definitions for categories 4-9 will be protocol specific.
- All conclusions should be based on all eligible patients.
- Subanalyses may then be performed on the basis of a subset of patients, excluding those for whom major protocol deviations have been identified (eg, early death due to other reasons, early discontinuation of treatment, major protocol violations, etc.). However, these subanalyses may not serve as the basis for drawing conclusions concerning treatment efficacy, and the reasons for excluding patients from the analysis should be clearly reported.
- The 95% confidence intervals should be provided.

## **Appendix D Handling and Shipment of Pharmacokinetic Samples**

Blood samples will be taken for pharmacokinetic evaluation by cannula or direct venipuncture at the time points listed in Appendix D-1 (dose escalation phase) and Appendix D-2 (dose expansion phase). The exact times and dates of blood sampling are to be recorded in the CRFs.

Blood samples (2 mL) for fruquintinib pharmacokinetics will be collected into sodium heparinate vacutainers. The tubes will be immediately inverted gently at least 5 times to mix the blood and then placed in ice bath prior to centrifugation. The tubes will be centrifuged at approximately 1000 g and 4°C for 10 minutes, after which the plasma will be transferred immediately into 2 clean prelabeled tubes. Approximately 0.5 mL plasma will be placed in each tube (Tube A and Tube B). After the tubes are tightly capped, the samples should be stored immediately at -20°C or -80°C. The whole process of plasma collection should be completed within 2 hours of the blood sampling. According to the present results of plasma stability, fruquintinib can be stored at -20°C and at -80°C for 133 days. For long-term storage, it is recommended that the plasma samples be stored at -80°C.

Each sample will be identified by date of collection, study number, patient number and initials, and sample time point identifier (i.e. 30 minutes, 1 hour, 4 hours etc.). Tube B samples must be labeled as “duplicate.”

All plasma samples will be shipped on dry ice to the central laboratory within 30 days of sample collection. The dry ice should be sufficient to keep the samples frozen during the whole shipment period. The samples of Tube B are shipped out after the prior batch of Tube A has been received safely by the central laboratory. Tube A samples will be used for bioanalysis. Tube B samples will be stored in -80°C freezer for future use. The laboratory should be notified at least 1 day prior to the arrival of the sample and be provided shipping details and tracking numbers for the shipment.

Prior to shipment, a PK sample requisition form (containing the details of each sample/label identification included in the shipment) will be prepared. All sample correspondence must contain the study number, study drug, and Site references (including emergency contact details and responsible shipment coordinator). All of the sample details on this log must match the details included on the individual sample labels, as each sample label will be checked against the list by Centre Laboratories' sample coordination personnel. The log should be reviewed by the preparer and a second individual for accuracy and signed/dated by both individuals. To avoid sample mix-ups or misidentification, the samples in the shipment will be sorted by patient number and sample time using segmented cartons.

**Table D-2 PK Sampling Time Points (Dose Escalation Phase and Cohort A of Dose Expansion Phase)**

Visit Cycle	Time Point
Cycle 1, Day 1	Pre-dose ( $\leq 10$ minutes)
	Post-dose 1 hour $\pm\pm(\pm 5$ minutes)
	Post-dose 2 hours $\pm\pm(\pm 15$ minutes)
	Post-dose 4 hours $\pm\pm(\pm 30$ minutes)
	Post-dose 8 hours $\pm\pm(\pm 60$ minutes)
Cycle 1, Day 2	Pre-dose ( $\leq 10$ minutes)
Cycle 1, Day 14	Pre-dose ( $\leq 10$ minutes)
	Post-dose 1 hour $\pm\pm(\pm 5$ minutes)
	Post-dose 2 hours $\pm\pm(\pm 15$ minutes)
	Post-dose 4 hours $\pm\pm(\pm 30$ minutes)
	Post-dose 8 hours $\pm\pm(\pm 60$ minutes)
Cycle1, Day 15	Pre-dose ( $\leq 10$ minutes)
Cycle1, Day 21	Pre-dose ( $\leq 10$ minutes)
	Post-dose 1 hour $\pm\pm(\pm 5$ minutes)
	Post-dose 2 hours $\pm\pm(\pm 15$ minutes)
	Post-dose 4 hours $\pm\pm(\pm 30$ minutes)
	Post-dose 8 hours $\pm\pm(\pm 60$ minutes)
Cycle 1, Day 22	Post-dose 24 hours $\pm\pm(\pm 60$ minutes) on Day 21

**Table D-2 PK Sampling Time Points (Cohort B, C, D, and E of Dose Expansion Phase)**

Visit Cycle	Time Point
Cycle 1, Day 1	Pre-dose ( $\leq 10$ minutes)
	Post-dose 1 hour $\pm\pm(\pm 5$ minutes)
	Post-dose 2 hours $\pm\pm(\pm 15$ minutes)
	Post-dose 4 hours $\pm\pm(\pm 30$ minutes)
	Post-dose 8 hours $\pm\pm(\pm 60$ minutes)
Cycle 1, Day 2	Pre-dose ( $\leq 10$ minutes)
Cycle 1, Day 14	Pre-dose ( $\leq 10$ minutes)
	Post-dose 1 hour $\pm\pm(\pm 5$ minutes)
	Post-dose 2 hours $\pm\pm(\pm 15$ minutes)
	Post-dose 4 hours $\pm\pm(\pm 30$ minutes)
	Post-dose 8 hours $\pm\pm(\pm 60$ minutes)
Cycle1, Day 15	Pre-dose ( $\leq 10$ minutes)

## Appendix E Prohibited Concomitant Medications that Have a Known Risk of QT prolongation and/or Torsades des Pointes (TdP)

The list is continuously updated online at [www.crediblemeds.org](http://www.crediblemeds.org) or [www.qtdrugs.org](http://www.qtdrugs.org)

Generic Name	Brand Names (Partial List)	Drug Class
Amiodarone	Cordarone, Pacerone, Nexterone	Antiarrhythmic
Anagrelide	Agrylin, Xagrid	Phosphodiesterase 3 inhibitor
Arsenic trioxide	Trisenox	Anticancer
Azithromycin	Zithromax, Zmax	Antibiotic
Chloroquine	Aralen	Antimalarial
Chlorpromazine	Thorazine, Largactil, Megaphen	Antipsychotic / Antiemetic
Cilostazol	Pletal	Phosphodiesterase 3 inhibitor
Ciprofloxacin	Cipro, Cipro-XR, Neofloxin	Antibiotic
Citalopram	Celexa, Cipramil	Antidepressant, SSRI
Clarithromycin	Biaxin, Prevpac	Antibiotic
Cocaine	Cocaine	Local anesthetic
Disopyramide	Norpace	Antiarrhythmic
Dofetilide	Tikosyn	Antiarrhythmic
Domperidone	Motilium, Motillium, Motinorm Costi, Nomit	Antinausea
Donepezil	Aricept	Cholinesterase inhibitor
Dronedarone	Multaq	Antiarrhythmic
Droperidol	Inapsine, Droleptan, Dridol, Xomolix	Antipsychotic / Antiemetic
Erythromycin	E.E.S., Robimycin, EMycin, Erymax, Ery-Tab, Eryc Ranbaxy, Erypar, Eryped, Erythrocin Stearate Filmtab, Erythrocot, E-Base, Erythroped, Ilosone, MY-E, Pediamycin, Zineryt, Abboticin, Abboticin-ES, Erycin, PCE Dispertab, Stiemycine, Acnasol, Tiloryth	Antibiotic
Escitalopram	Ciprallex, Lexapro, Nexito,	Antidepressant, SSRI
Flecainide	Tambocor, Almarytm, Apocard, Ecrinal, Flécaine	Antiarrhythmic
Fluconazole	Diflucan, Trican	Antifungal
Haloperidol	Haldol	Antipsychotic
Ibutilide	Corvert	Antiarrhythmic
Levofloxacin	Levaquin, Tavanic	Antibiotic
Methadone	Dolophine, Symoron, Amidone, Methadose, Physeptone, Heptadon	Opioid agonist

Generic Name	Brand Names (Partial List)	Drug Class
Moxifloxacin	Avelox, Avalox, Avelon	Antibiotic
Ondansetron	Zofran, Anset, Ondemet, Zuplenz, Emetron, Ondavell, Emeset, Ondisolv, Setronax	Antiemetic
Oxaliplatin	Eloxatin	Antineoplastic Agent
Papaverine HCl (Intra-coronary)	none	Vasodilator, Coronary
Pentamidine	Pentam	Antifungal
Pimozide	Orap	Antipsychotic
Procainamide	Pronestyl, Procan	Antiarrhythmic
Propofol	Diprivan, Propoven	Anesthetic, general
Quinidine	Quinaglute, Duraquin, Quinact, Quinidex, Cin-Quin, Quinora	Antiarrhythmic
Sevoflurane	Ultane, Sojourn	Anesthetic, general
Sotalol	Betapace, Sotalex, Sotacor	Antiarrhythmic
Thioridazine	Mellaril, Novoridazine, Thioril	Antipsychotic
Vandetanib	Caprelsa	Anticancer

**Source:** [www.crediblemeds.org](http://www.crediblemeds.org) or [www.qt.drugs.org](http://www.qt.drugs.org)

## Appendix F Fruquintinib and Concomitant Medication

Fruquintinib is not a substrate of efflux transporters. Fruquintinib showed dose-dependent inhibition on P-glycoprotein (P-gp) and breast cancer resistance protein (BCRP). Based on the data for digoxin transport (mediated by P-gp) and estrone-3-sulfate transport (mediated by BCRP), the  $IC_{50}$  on P-gp and BCRP was estimated to be 4.60 and 1.29  $\mu$ M, respectively.

According to the present metabolism data, cytochrome P450 enzymes CYP3A4/5 play an important role in the metabolism of fruquintinib. Fruquintinib had no marked reversibly inhibitory effects on CYPs 1A2, 2B6, 2C8, 2C9, 2C19, 2D6, and 3A4/5 ( $IC_{50} > 10 \mu$ M) and no induction of CYP1A2, [REDACTED] and CYP3A4 at the tested concentration of 10  $\mu$ M. No marked time-dependent inhibition was observed for CYP1A2, 2B6, 2C8, 2C9, 2C19, 2D6, and 3A4/5.

A series of CYP3A4 strong inducers and strong inhibitors are listed in Tables F-1 and F2 below. Patients who received a CYP3A4 strong inducer or strong inhibitor within 2 weeks (3 weeks for hyperforin perforatum treatment) prior to the first dose of the study drug will not be allowed to participate in the study.

Typical substrates of P-gp and BCRP are listed in Table F-3 below. During the study, substrates of P-gp and BCRP, and strong inducers and inhibitors of CYP3A4/5 are avoided to be administered concomitantly with fruquintinib, unless investigators consider it necessary. In this case, efficacy reduction and toxicity increases resulting from the interaction should be closely monitored.

Not all the medications are listed in the following tables. Other drugs known to possibly affect CYP3A4 activity and to be substrates of P-gp and BCRP should be used with cautions. When combining fruquintinib with other drugs the prescription information of all concomitant medications should be reviewed.

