14. Clinically significant cardiovascular disease, including but not limited to acute myocardial infarction or coronary artery bypass surgery within 6 months prior to enrollment, severe or unstable angina pectoris, New York Heart Association Class III/IV congestive heart failure, ventricular arrhythmias requiring treatment, or left ventricular ejection fraction (LVEF) <50%;
15. Mean corrected QT interval (QTc) using the Fridericia method (QTcF) >480 msec or any factors that increase the risk of QTc prolongation or risk of arrhythmic events such as hypokalemia, congenital long QT syndrome, family history of long QT syndrome, or unexplained sudden death under 40 years of age in a first-degree relative.
16. Concomitant medications with a known risk of causing QT prolongation and/or torsade de pointes (see list in [Appendix E](#); source list is continuously updated online at [www.qtdrugs.org](http://www.qtdrugs.org));
17. Patients who have ever received a VEGFR inhibitor, **except** for patients with mCRC enrolled in the dose expansion phase;
18. Systemic anti-neoplastic therapies (except for those described in Exclusion 18) or any investigational therapy within 4 weeks prior to the first dose of study drug, including chemotherapy, radical radiotherapy, hormone therapy, biotherapy and immunotherapy;
19. Systemic small molecule targeted therapies (eg, tyrosine kinase inhibitors) within 5 half-lives or 4 weeks (whichever is shorter) prior to the first dose of study drug;
20. Palliative radiotherapy for bone metastasis/lesion within 2 weeks prior to the initiation of study drug;
21. Brachytherapy (ie, implantation of radioactive seeds) within 60 days prior to the first dose of study drug;
22. Use of strong inducers or inhibitors of CYP3A4 within 2 weeks before the first dose of study drug (3 weeks for St John's Wort); P-glycoprotein (P-gp) or breast cancer resistance protein (BCRP) substrate within 2 weeks before the first dose of study drug (see [Appendix F](#) for a list of such medications);
23. Surgery or invasive procedure (ie, procedure that includes a biopsy) within 60 days prior to the first dose of study drug or unhealed surgical incision;
24. Any unresolved toxicities from a previous antitumor treatment greater than

CTCAE v 4.03 Grade 1 (except for alopecia);

25. Known human immunodeficiency virus (HIV) infection;

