### 5.3.2 Excluded Therapies

Any therapy intended for the treatment of cancer (with the exceptions as noted above), whether currently marketed or experimental, is prohibited. This includes, but is not limited to, the following: chemotherapy, hormonal therapy, biologic therapy, radiotherapy, or herbal therapy.

Prophylactic antiemetic, granulocyte colony stimulating factors, granulocyte macrophage colony-stimulating factors, platelet stimulating factors or erythropoietin are not allowed during the DLT observation period in the dose escalation phase.

Concomitant use of acid-reducing agents (eg, proton pump inhibitors, histamine receptor antagonists, antacids) during the dose escalation phase should be avoided as those agents may interfere with identifying reliable MTD and/or RP2D.

Concomitant use of medications that have a known risk of causing QT prolongation and/or torsade de pointes (see “combined” list at <http://www.qtdrugs.org>, with attention to those drugs listed as KR (“known risk”).

Palliative radiation for symptom control is allowed provided it does not compromise tumor assessments of target lesions. However, fruquintinib treatment should be suspended during the radiation period and not resumed until at least 7 days after radiation only after meeting the following criteria:

- Radiation related toxicities resolves to  $\leq$ Grade 2;
- No disease progression observed.

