### 5.3.3 Drug-Drug Interactions

The potential of pharmacokinetic drug-drug interaction was tested *in vitro*. Fruquintinib was not a substrate of efflux transporters. Fruquintinib showed dose-dependent inhibition on P-gp and BCRP. Based on the data for digoxin transport (mediated by P-gp) and estrone-3-sulfate transport (mediated by BCRP), the IC50 on P-gp and BCRP was estimated to be 4.60 and 1.29 μM, respectively.

According to the present metabolism data, enzymes CYP3A4/5 play an important role in the metabolism of fruquintinib. Fruquintinib had no marked inhibitory effects on CYPs 1A2, 2B6, 2C8, 2C9, 2C19, 2D6, and 3A4/5 (IC50 >10 μM) and no induction of CYP1A2, [REDACTED] and CYP3A4 at the tested concentration of 10 μM. No marked time-dependent inhibition was observed for CYPs 1A2, 2B6, 2C8, 2C9, 2C19, 2D6, and 3A4/5.

Substrates of P-gp and BCRP, and inducers and inhibitors of CYP3A4/5 should not be administered concomitantly with fruquintinib, unless investigators consider it necessary. In this case, efficacy reduction and toxicity increases resulting from the interaction should be closely monitored. Examples of the medicines to avoid are listed in [Appendix F](#).

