**Table F-1 Typical Strong Inhibitors of CYP3A4**

Strong Inhibitors of CYP3A4
Boceprevir
Clarithromycin
Conivaptan
Elvitegravir/Ritonavir
Fluconazole
Grapefruit juice a,b
Indinavir
Itraconazole
Ketoconazole
Lopinavir/Ritonavir
Mibefradil
Nelfinavir
Posaconazole
Ritonavir
Saquinavir
Telaprevir
Telithromycin
Tipranavir/Ritonavir
Troleandomycin
Voriconazole

a Super-concentrated grapefruit juice

b During the study, patients should not consume large amounts of grapefruit or lime (or products that include these fruits, such as grapefruit juice and orange jam). No more than one cup (120 mL) of grapefruit juice, half a grapefruit or a spoon full (15 g) of orange jam should be consumed each day.

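### Clarithromycin and fluconazole fall under two different on-study rules with no stated precedence, and section 5.3.3 and Appendix F differ on which CYP3A4/5 inhibitors and inducers are to be avoided

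*Protocol*

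**What the plan says.** Four places in the protocol bear on what may be given alongside fruquintinib.

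- **Appendix E** is headed "Prohibited Concomitant Medications that Have a Known Risk of QT prolongation and/or Torsades des Pointes (TdP", with the bracket closing after the abbreviation. It lists clarithromycin (brand names "Biaxin, Prevpac") and fluconazole ("Diflucan, Trican"). It has no investigator-discretion clause.
- **Section 5.3.2, Excluded Therapies**, has a sentence that opens "Concomitant use of medications that have a known risk of causing QT prolongation and/or torsade de pointes", adds a bracketed pointer to a website list, and stops. It never says what is required, and it does not cite Appendix E.
- **Section 5.3.3, Drug-Drug Interactions**, says that "inducers and inhibitors of CYP3A4/5 should not be administered concomitantly with fruquintinib, unless investigators consider it necessary". It does not limit this by potency, and it sends the reader to Appendix F for examples.
- **Appendix F** says that during the study "strong inducers and inhibitors of CYP3A4/5 are avoided to be administered concomitantly with fruquintinib, unless investigators consider it necessary", with closer monitoring when they are used. Its list of "Typical Strong Inhibitors of CYP3A4" (Table F-1) includes both clarithromycin and fluconazole. It adds that the tables are incomplete and that other drugs which may affect CYP3A4 call for caution.

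Two entry criteria touch the same drugs. Exclusion 16 bars "Concomitant medications with a known risk of causing QT prolongation and/or torsade de pointes" and cites Appendix E. Exclusion 22 sets a two-week washout for strong CYP3A4 inhibitors and inducers (three weeks for St John's Wort).

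**The concern.** A site that has to treat an infection during the study can look up clarithromycin or fluconazole and find it prohibited in one appendix and left to the investigator's judgement in the next. Neither appendix refers to the other. For a less potent CYP3A4 inhibitor or inducer, the same site finds a stricter instruction in section 5.3.3 than in Appendix F.

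The stake is mainly patient safety. By the protocol's own lists, these two drugs combine a known QT risk with strong inhibition of CYP3A4, and sections 5.3.3 and Appendix F both say that CYP3A4/5 are important in fruquintinib metabolism. There is a lesser stake in the data. Cycle 1 PK parameters are a secondary endpoint, and the timed ECGs on Days 1 and 15 are taken to examine the relation between concentration and QT (Appendix A, note 15). The PK analysis set keeps every dosed patient with at least one analysed sample (section 8.1).

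**Working it through.** No arithmetic applies. The check is a cross-match of the lists and a comparison of the rules.

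**Step 1: which drugs are on both lists.** Appendix E was compared with Tables F-1, F-2 and F-3. Clarithromycin and fluconazole are in both Appendix E and Table F-1. No Appendix E drug is in Table F-2 (strong inducers) or Table F-3 (P-gp and BCRP substrates). The overlap is exactly two drugs, one an antibiotic and one an antifungal.

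**Step 2: the rules for those two drugs.**

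| Place | Stage | Rule | Discretion |
|---|---|---|---|
| Exclusion 16 | Entry | Excluded (QT) | None |
| Exclusion 22 | Entry | Two-week washout (strong CYP3A4) | None |
| Section 5.3.2 | On study | Sentence incomplete; sits under Excluded Therapies | None stated |
| Appendix E | Stage not stated | Prohibited, by its title | None |
| Section 5.3.3 | On study | Not to be given with fruquintinib | Yes, if judged necessary |
| Appendix F | On study | Avoided | Yes, if judged necessary |

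At entry the position is clear: both criteria keep the two drugs out. On study, the prohibition rests on a section heading, an appendix title and, by extension, an entry criterion, while the discretion is written out in full sentences in two places. No passage says which prevails.

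**Step 3: the scope of the CYP3A4 rule.**

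| Place | Strong agents | Other agents |
|---|---|---|
| Exclusion 22 | Washout | Not mentioned |
| Section 5.3.3 | Avoid unless necessary | Avoid unless necessary |
| Appendix F | Avoid unless necessary | Use with caution |

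The Appendix F phrase could be parsed as strong inducers and any inhibitors. The titles of Tables F-1 and F-2, the appendix's own washout sentence and its separate caution sentence all point to strong as qualifying both. On that reading, section 5.3.3 and Appendix F agree for strong agents and differ for the rest, even though one refers to the other for examples.

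**Step 4: reach into the data.** For Cohorts B to E, the PK samples fall on Days 1, 2, 14 and 15 of Cycle 1; the dose escalation phase and Cohort A add Days 21 and 22. The timed ECGs are on Days 1 and 15. Because of the two entry criteria, either drug could affect these measurements only if newly started between first dose and the last sampling day.

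**The case against.** The best defence is that the two appendices deal with different hazards. Appendix E is about QT prolongation; Appendix F is about metabolic and transporter interactions, and its discretion is tied to monitoring the effects of the interaction. Restrictions set on separate grounds are ordinarily cumulative, so a careful reader could hold that the QT prohibition stands whatever Appendix F allows. The heading of section 5.3.2, the title of Appendix E and exclusion 16 also leave little doubt about what the incomplete sentence was meant to say.

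This has force. A reader might infer a flat contradiction, with the protocol expressly permitting what it prohibits; the documents do not go that far, because Appendix F never says that it lifts the QT restriction. But the protocol does not state the cumulative reading either, and a site that consults only section 5.3.3 or Appendix F is given discretion with no warning that another list applies.

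Three further inferences are tempting and not supported.

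- A patient on a non-strong CYP3A4 inhibitor might seem to fall outside Appendix F. Its caution sentence covers such drugs.
- The same patient might seem to be in breach of section 5.3.3 from Day 1. That section has its own discretion clause, so continued use judged necessary by the investigator complies with it. What remains is a difference of degree between avoiding and using with caution.
- The 25.1% infection rate in Table 3 might be used to estimate how many patients are affected. It counts any infection at any time and says nothing about use of either drug.

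The data consequence is also limited: the Cycle 1 window is short, entry is guarded twice, and the SAP states that PK analysis is outside its scope, so how affected profiles would be handled cannot be judged from these documents.

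**Conclusion.** The point holds as an inconsistency of wording on a safety matter. Two drugs have a prohibition and a discretionary rule with no order of precedence, the on-study QT sentence is unfinished, and the potency scope differs between section 5.3.3 and Appendix F. This is more than missing detail, because sites could follow the text in good faith and act differently.

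The number of patients affected is unknown. No efficacy endpoint, sample size or planned efficacy analysis changes. The conclusion rests on reading strong in Appendix F as qualifying both inducers and inhibitors, which bears only on the potency part. The finding on the two drugs does not depend on it.

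**What to change.** Reconcile sections 5.3.2 and 5.3.3 with Appendices E and F so that one on-study rule results. In particular:

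- state which list governs a drug that appears on both;
- complete the sentence on QT drugs in section 5.3.2 and have it cite Appendix E;
- use the same potency wording in section 5.3.3, Appendix F and exclusion 22.

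Which rule applies is for the sponsor's clinical team. The same pass could pick up the grapefruit juice footnote to Table F-1, which sets a daily limit where section 5.1.6 lists grapefruit juice as prohibited.

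Optionally, flag Cycle 1 PK profiles and timed ECGs taken while a listed drug was in use.

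The cost is a protocol clarification or amendment. The optional flag needs no new data, since concomitant medication is already collected (Appendix A, note 5) and listed (SAP section 14.1).
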